12.1.4 Exit Visit

NOTE: All VA measurements MUST be made using a phoropter.

- NOTE: If a subject requires further follow-up on an AE/SAE upon discontinuation or completion of 3-Month Visit, the Investigator must schedule Unscheduled Visits to follow up as necessary. At these unscheduled follow-up visits, the subject should remove contact lenses s/he may be wearing. At a minimum, a slit lamp examination, keratometry, spherocylindrical refraction, and distance BSCVA should be completed. The Investigator is required to follow the subject until the condition no longer warrants further follow-up for study purposes. An Unscheduled Visit eCRF must be completed for each of these follow-up visits.
 - a. Indicate status of the subject on the Subject Exit Form. If the status is "Discontinued" or "Non-dispensed," indicate the PRIMARY exit reason for each eye on the Subject Exit Form.
 - b. Collect/assess all AEs, including serious or significant non-serious AEs.
 - c. Collect study lens from subject and record in Product Accountability Log.
 - d. For all subjects, complete an exit ocular examination without lenses on the eyes. Collect the following assessments at the 3-Month Visit or at the Exit Visit:
 - Spherocylindrical refraction
 - Distance BSCVA
 - Keratometry
 - e. For each eye, compare the final visit distance BSCVA to the distance BSCVA obtained at the Screening Visit. If the VA has decreased by ≥10 letters (0.2 logMAR), explain.
 - f. For each eye, compare the final visit keratometry readings to the Screening Visit keratometry readings. If there is a change of ≥ 1.00 D, explain.
 - g. The Subject Exit eCRF should be completed.

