9.2.3 Subject Discontinuation

A subject MAY be discontinued (at the discretion of the Investigator, the Sponsor, and/or the IRB) prior to the final study visit for a variety of reasons, including, but not limited to:

- An adverse event (AE) occurring during the course of the study, which precludes continued treatment or follow-up
- Persistent Grade 3 or 4 slit lamp findings (must be reported to the Sponsor within 24 hours)
- Persistent study-related symptoms/complaints

A subject MUST be discontinued prior to the final study visit (3-Month Visit [Visit 6]) for any of the following reasons:

- Voluntary withdrawal
- Death
- Investigator decision that it is not in the best medical interest of the subject to continue participation in the investigation
- Ineligible after randomization a subject who was enrolled but was later found to have not met the eligibility criteria in the protocol
- Inability to maintain recommended wearing schedule
- Continued failure to follow subject instructions
- Misses more than one consecutive follow-up visit
- Lack of motivation
- Lost to follow-up (refer to Section 9.2.4)
- Instillation of non-medically indicated solution not specified in the protocol
- Other eye is discontinued
- Becomes pregnant during the study

Prior to discontinuing a subject, every effort should be made to contact the subject, schedule an Exit Visit, obtain as much follow-up data as possible, and retrieve all study materials. Adverse events will be followed as described in Section 13.0. Subject

discontinuations will be documented clearly on the source document and applicable eCRF. The Investigator should indicate the PRIMARY (one) reason that the subject was discontinued for each eye. Subjects who are discontinued from the study following randomization will not be replaced.

Exit Visit assessments should be completed for discontinued subjects.

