9.4 Study Duration

Subjects will be followed for 3 months after dispensing (unless discontinued or lost to follow-up) and must adhere to the following schedule:

Table 1. Schedule of Visits

Visit Number	Visit Name	Target	Acceptable Visit Range
1	Screening Visit	None	Day -30 to Day-7
2	Dispensing Visit	Day 1	Not applicable
3	1-Week Visit	Day 8	Day 5 – 9
4	1-Month Visit	Day 31	Day 27 – 35
5	2-Month Visit	Day 61	Day 54 – 68
6	3-Month Visit	Day 92	Day 91* – 101

^{*}CRITICAL NOTE: The 3-Month Visit must occur no earlier than Day 91.

The visit range is based on the date test lenses are initially dispensed (Dispensing Visit). A visit scheduling table will be provided in the initial study shipment to aid the Investigator in scheduling follow-up visits.

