13.1.1 Adverse Events

An adverse event (AE) is any untoward medical occurrence, unintended disease or injury, or untoward clinical signs (including abnormal laboratory findings) in a subject, user, or other persons, whether or not related to the investigational medical device. This definition includes events related to the investigational medical device, comparator, or the procedures involved. For users or other persons, this definition is restricted to events related to investigational medical devices.

Throughout the course of this study, all efforts will be made to remain alert to possible AEs. The term "AEs" includes both SAEs and significant non-serious AE. Each are defined below.

If an AE occurs, the first concern will be the safety of the subject and appropriate medical intervention will be made. All AEs (SAEs and significant non-serious AEs) that occur will be reported in this study.

AEs should be differentiated into device related and non-device related. Any corneal infiltrate, ulcer, neovascularization, etc. shall be presumed to be device related, in the absence of an alternative explanation.

All AEs occurring after signing of informed consent and through the subject's end of participation in the study must be reported. All AEs must be followed until the event resolves or stabilizes.

All AEs should be photo documented and communicated to the CRO and Sponsor in electronic form.

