APPENDIX A: SCHEDULE OF VISITS AND PARAMETERS

All study tasks should be performed by qualified study site personnel as indicated on the delegation of authority log under the supervision of the Principal Investigator.

	Screening	Dispensing	1-Week	1-Month	2-Month	3-Month	
DDO CEDUDE / A COROCINENTEC	Visit 1	Visit 2	Visit 3	Visit 4	Visit 5	Visit 6	Exit
PROCEDURE/ASSESSMENTS	Day -30 to -7	Day 1	Day 5-9	Day 27-35	Day 54-68	Day 91-101 ^a	Visit
Informed consent/HIPAA authorization	X						 
Demographics/baseline eye/lens characteristics	X						
Contact lens use history and use ^b	X		X	X	X	X	
Medical history	X						
Eligibility	X						
Randomization	X						
Dispense and/or return study materials		X					X
Symptoms/complaints and subjective assessments (including rewetting drops [Yes/No])	X	X	X	X	X	X	
Adverse events	X	X	X	X	X	X	X
Without lenses							
Spherocylindrical refraction	X						X
Distance BSCVA	X						X
Keratometry	X						X
Slit lamp exam	X	X	X	X	X	X	
Keratometry comparison (Exit Visit to Screening Visit)							X
With study lenses							
Distance high-contrast logMAR lens VA		X	X	X	X	X	
Over-refraction and distance VA		X	X	X	X	X	
Lens wettability/centration/movement		X	X	X	X	X	
Lens deposits		X	X	X	X	X	
VA line change comparison							
Distance high-contrast logMAR lens VA at Visit 2 to distance BSCVA at Visit 1		X					
Distance BSCVA at Exit Visit to Distance BSCVA at Visit 1							X
Distance high-contrast logMAR lens VA at Visit 3-6 to distance high-contrast logMAR			X	X	X	Х	
lens VA at Visit 2							
Distance high-contrast logMAR lens VA at Visit 3-6 to distance BSCVA at Visit 1			X	X	X	X	

Page A-1 of 69

a. The 3-Month Visit MUST occur no earlier than Day 91.b. Contact lens use history is taken at the Screening Visit and contact lens use is taken at each of the follow-up visits.

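### A stand-alone Exit Visit requires no slit lamp examination and is not named for the primary safety endpoint, so some early leavers have no required slit lamp at last contact

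*Combined protocol and SAP*

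**What the plan says.** Section 9.2.3 sends early leavers to the exit assessments: "Exit Visit assessments should be completed for discontinued subjects". Those assessments are in 12.1.4(d): "For all subjects, complete an exit ocular examination without lenses on the eyes". The list that follows has three items: spherocylindrical refraction, distance BSCVA and keratometry.

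Appendix A agrees. Its row "Slit lamp exam" is marked for Visits 1 to 6 and blank in the Exit column, while the three listed assessments are marked for Exit.

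Step (b) of 12.1.4 reads "Collect/assess all AEs, including serious or significant non-serious AEs". A note in 12.1.4 makes a slit lamp part of the minimum examination at unscheduled visits held to follow up an adverse event after exit.

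Section 14.7.1.3 classifies each eye by whether it had a Grade >2 slit lamp finding at any follow-up visit. It names the 1-Week, 1-Month, 2-Month and 3-Month Visits and, optionally, unscheduled visits. It does not name the Exit Visit. The safety population in 14.6.3 is all dispensed eyes.

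**The concern.** The primary safety endpoint is read from the slit lamp. At a stand-alone Exit Visit the site is not required to use one, so a Grade >2 finding present at last contact need not be looked for, although the eye stays in the safety population.

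The same visit asks for all adverse events. Some of these are signs defined without any symptom: neovascularization in the central 6 mm (serious, 13.1.5) and corneal staining of Grade 3 or higher (significant non-serious, 13.1.6). At Visits 3 to 6 the protocol has sites note staining and central neovascularization under the slit lamp step (12.1.3(e)). At exit the slit lamp becomes mandatory only once adverse event follow-up is already known to be needed, so the step that might reveal the need is missing.

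**Working it through.** **Who is affected.** Taking the routes out of the study in turn:

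- On-time completers: exit is combined with the 3-Month Visit, which has a slit lamp (12.1.3). Not affected.
- Subjects who exit at the Dispensing Visit or at another scheduled visit: slit lamp done there. Not affected.
- Subjects with problems, or in adverse event follow-up: slit lamp required (12.1.5, 12.1.4 note). Not affected.
- Lost to follow-up: no last contact at which to examine. Not affected, and not helped by any fix.
- Dispensed subjects with no recognised problem who leave between scheduled visits, for example by "Voluntary withdrawal", and attend only an Exit Visit: **affected**.
- Dispensed subjects with no recognised problem who are discontinued for missing more than one consecutive follow-up visit (9.2.3) and attend only an Exit Visit: **affected**.

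**Time since the last required slit lamp.** From Table 1, assuming every earlier visit was in range and the subject leaves before the next range opens. Longest gap = day before the next range opens − earliest in-range day of the last visit.

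| Last visit attended | Calculation | Longest gap |
|---|---|---|
| Dispensing | Day 4 − Day 1 | 3 days |
| 1-Week | Day 26 − Day 5 | 21 days |
| 1-Month | Day 53 − Day 27 | 26 days |
| 2-Month | Day 90 − Day 54 | 36 days |

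These are conditional figures. After missed visits the gap can be longer. In the first row the Dispensing slit lamp precedes lens insertion (12.1.2), so such an eye has no required slit lamp after any study lens wear.

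**How such an eye would be counted.** An eye with an earlier clean follow-up slit lamp stays 'No'. For an eye with none after dispensing, 14.7.1.3 says each eye is classified Yes or No, whereas 14.7.1.1 uses non-missing denominators and 14.7.4 does not impute. The protocol does not settle whether the eye is 'No' or missing.

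**The plan's own figures.** Section 14.4.2 states 99% power with 100 test and 50 control eyes at 0.012 in both arms. Exact binomial enumeration with the Newcombe-Wilson limit gives 99.9%. Enrolment also reproduces: 75/0.9 = 83.3, so 84 subjects or 168 eyes (14.4.3). Nothing here disputes these figures.

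**Possible effect on the conclusion (illustration).** Upper limit = p_T − p_C + √[(u_T − p_T)² + (p_C − l_C)²], where u and l are Wilson limits with z = 1.645. The test lens passes if the limit is ≤ 0.10, or if both arms have no events. With 112 v 56 eyes and no control events:

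- 5 test events: limit 0.0889, pass.
- 6 test events: p_T = 6/112 = 0.0536, u_T = 0.1003, p_C = l_C = 0, so the limit is 0.0536 + (0.1003 − 0.0536) = 0.1003, fail.

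The documents do not say how losses divide by type, so the illustration lets all planned losses go unseen: 168 × 0.10 = 16.8 eyes, split 2:1 as 11.2 test and 5.6 control.

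- Independent eyes, as 14.7.1.1 assumes: 11 v 6 unseen, leaving 101 v 50 seen.
- Fully concordant eyes within a subject: whole subjects, so 12 v 6 eyes (6 v 3 subjects) unseen and 100 v 50 eyes (50 v 25 subjects) seen.

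Seen eyes have the rate 0.012. Unseen eyes have the rate shown, equal in both arms. The table gives the probability that the observed result passes and the full result fails.

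| Unseen rate | Independent eyes | Fully concordant eyes |
|---|---|---|
| 0.012 (plan) | about 0.05% | about 0.5% |
| 5% (assumed) | about 0.3% | about 2.5% |

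The results are about the same whether unseen eyes are counted as 'No' or left out.

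**The case against.** The strongest reply is that this is a consistent and minor design choice. Section 12.1.4(d) and Appendix A agree, so nothing is contradictory. Exit is usually attached to a visit that has a slit lamp, and leavers most likely to carry a Grade >2 sign, those with adverse events or problems, are sent to visits that require one. The words about an exit ocular examination are general, and 9.2.3 asks sites to "obtain as much follow-up data as possible". On counting, the phrase about any follow-up visit could be taken to include the Exit Visit, and the formal SAP announced in 14.7 may say so.

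Much of this stands. The group is narrow, its size is unknown, and naming the Exit Visit in 14.7.1.3 is largely a matter of wording. The formal SAP was not in the text reviewed, so the counting point is limited to 14.7.1.3. But neither general phrase makes a slit lamp compulsory, and the item list and the schedule both leave it out. A SAP cannot supply an examination that was not done.

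A reader might infer three stronger things that the documents do not support. First, that early leavers in general go unexamined: most routes out include a slit lamp. Second, that unexamined eyes will certainly be dropped, or certainly be counted as 'No': the protocol leaves this open. Third, that the non-inferiority result is in danger: that would need Grade >2 rates among apparently problem-free leavers far above the planned 0.012, or a rise in one arm only, and nothing in the documents suggests either.

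**Conclusion.** The gap is real and narrow. A dispensed subject with no recognised problem who attends only a stand-alone Exit Visit has no required slit lamp at last contact, and 14.7.1.3 does not say that one done there would count. The case for change is safety ascertainment at the last contact, where adverse events are to be collected.

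The effect on the non-inferiority conclusion is probably small. The percentages are an illustration and not an upper bound. They rest on all planned losses going unseen, equal unseen rates in the two arms, an assumed 5% in the second row, and either independence or complete concordance of a subject's eyes. Full concordance is an extreme, but it raises the figures about tenfold, so the independent-eye figures should not be taken as limits. Losses that were examined, never dispensed or never seen again would reduce the number of eyes that an exit slit lamp could recover.

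**What to change.** 1. In 12.1.4(d) and the Exit column of Appendix A, add the graded slit lamp examination used at Visits 1 to 6 for any dispensed subject whose Exit Visit is not combined with a visit that already includes one.
2. In 14.7.1.3, name the Exit Visit among the follow-up visits counted for the primary safety endpoint.

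The cost is one short routine examination for a few early leavers, one field on the exit form and one phrase in the analysis section. The sample size does not change. The change does not help subjects lost to follow-up.

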12.1.5 Unscheduled Visits

Additional visits may be scheduled, as necessary, to ensure the safety and well-being of subjects. All additional exams should be fully documented in the source documents and on Unscheduled Visit eCRFs, as appropriate. Visits intended to fulfill scheduled visit requirements that fall outside the designated scheduled visit range, are not Unscheduled Visits. In these cases, the visit data will be collected and transcribed to the appropriate scheduled visit eCRF.

If a subject is seen for multiple visits during a given visit timeframe, the data from the visit that is intended to meet the protocol requirements for the scheduled visit should be captured on the visit eCRF. Where such a determination cannot be made, the first visit

within the scheduled visit interval will be used for completion of the protocol-required scheduled visit eCRF. Data from any additional visits within a scheduled visit interval will be captured on an Unscheduled Visit eCRF.

12.1.5.1 Product Dispensing Only (Part of the Unscheduled Visit - used only if lens replacement is needed)

If a subject is only seen for an unscheduled lens replacement, a complete exam is not required as long as the subject is not experiencing any problems. In an effort to ensure the Investigator remains masked, an unmasked designee MUST dispense the lens(es) to the subject. Record lenses dispensed in the Product Accountability Log.

- 12.1.5.1.1. If study lenses are dispensed, collect the following information in the source document and transcribe to the Product Dispensing Only eCRF Form:
 - Visit date
 - Subject ID number
 - Subject initials
 - Primary reason for lens replacement
 - Dispensed lens power
- 12.1.5.2 If any assessment is performed, then an Unscheduled Visit Form must be completed instead of a Product Dispensing Only Form.

NOTE: All worn study lenses are to be returned to the Sponsor at the end of the study as directed with the materials provided. Worn lenses will be dry stacked in lens cases and returned to Bausch and Lomb. All contact lenses must be accompanied by a CTM Product Accountability Log.

If a subject is experiencing problems, complete the following:

- a. Indicate the reason for the Unscheduled Visit.
- b. Collect/assess all AEs, including serious or significant non-serious AEs.
- c. Collect Symptoms/Complaints and Subjective Assessment information.
- d. Evaluate the lenses (while on eye) and record the following assessments in the source documentation and eCRF:
 - Distance high-contrast logMAR lens VA
 - Over-refraction and distance VA
 - Lens wettability, centration and movement
 - Lens deposits

For each eye, compare the distance high-contrast logMAR lens VA to the distance BSCVA obtained at the Screening Visit. If the VA has decreased by ≥ 10 letters (0.2 logMAR), record in the subject's source document and explain.

e. Perform the following assessments without lenses and record in the subject's source document: spherocylindrical refraction, distance BSCVA, and keratometry.

- f. Perform a slit lamp examination (without lenses). Record all slit lamp findings and, at a minimum, sketch the following in the subject's source document:
 - Any ungraded finding marked as "PRESENT"
 - Any new corneal scars
 - Any neovascularization within the central 6 mm of the cornea
 - Any corneal staining
 - Any corneal infiltrate (record details on the Corneal Infiltrates Evaluation Form [APPENDIX C])
 - Any other graded slit lamp findings Grade ≥2
- g. For female subjects, re-emphasize the exclusion criterion stating that if the subject is of childbearing potential and is pregnant and or breast feeding, she is ineligible to be a part of the study.
- h. If the subject is discontinued or exited at this visit, the Exit Visit Form should also be completed.

12.1.6 Missed Visits

If a subject misses any scheduled follow-up visit and cannot be seen prior to the start of the visit range for the next scheduled follow-up visit, the visit is considered missed. Indicate a missed visit on the eCRF for that scheduled visit.

12.2 Study Completion

Bausch + Lomb Global Clinical Operations will notify the Investigator when to contact the IRB to inform them that the study is complete.

12.2.1 Study Termination/Suspension

If during the study it becomes evident to the Sponsor that the study should be stopped prematurely or placed on hold, appropriate notification will be given to the Investigator(s) and IRBs, and US Food and Drug Administration (FDA) or Local Health Authority, as applicable. Bausch + Lomb Global Clinical Operations will instruct the Investigators to stop/restart dispensing study materials and will arrange for study closeout, if applicable, at each site.

12.3 Concomitant Medications/Therapy

Other contact lenses/solutions are not allowed to be used by subjects during the study.

Ocular medications or systemic or topical medications that, in the Investigator's opinion, could potentially affect ocular physiology or lens performance are also prohibited, unless medically necessary during the course of the study. If used during the course of the study, these medications must be reported in the source and the appropriate eCRF.

12.4 Treatment Compliance

The Investigator or other designee will review instructions and warnings for lens wear, lens care, handling, cleaning, and disinfecting with the subject. Any subject who does not

follow instructions to a degree that, in the Sponsor or Investigator's opinion, jeopardizes the subject's well-being or the validity of the study must be discontinued.

12.5 Protocol Deviations

The date of and reason for deviations will be documented in all cases. Significant or major protocol deviations impacting the safety of the subject or the integrity of the study must be reported by the Investigator to the IRB immediately. Reporting of all other protocol deviations must adhere to the requirements of the governing IRB.

Subjects may continue to participate until the end of the study, unless the protocol deviations put the subject at risk or the subject's condition requires that they be discontinued from the study.

13.0 ADVERSE EVENTS

13.1 Adverse Event Definitions

For the purposes of this study, AEs include ocular AEs in the study eye(s), all ocular and non-ocular serious adverse events (SAEs), adverse device effects (ADEs), and unanticipated adverse device effects (UADEs). AEs, SAEs, ADEs, and UADEs are defined as follows:

13.1.1 Adverse Events

An adverse event (AE) is any untoward medical occurrence, unintended disease or injury, or untoward clinical signs (including abnormal laboratory findings) in a subject, user, or other persons, whether or not related to the investigational medical device. This definition includes events related to the investigational medical device, comparator, or the procedures involved. For users or other persons, this definition is restricted to events related to investigational medical devices.

Throughout the course of this study, all efforts will be made to remain alert to possible AEs. The term "AEs" includes both SAEs and significant non-serious AE. Each are defined below.

If an AE occurs, the first concern will be the safety of the subject and appropriate medical intervention will be made. All AEs (SAEs and significant non-serious AEs) that occur will be reported in this study.

AEs should be differentiated into device related and non-device related. Any corneal infiltrate, ulcer, neovascularization, etc. shall be presumed to be device related, in the absence of an alternative explanation.

All AEs occurring after signing of informed consent and through the subject's end of participation in the study must be reported. All AEs must be followed until the event resolves or stabilizes.

All AEs should be photo documented and communicated to the CRO and Sponsor in electronic form.

